8. STATISTICS

8.1. Description of the planned statistical methods

The planned analysis will take place in 3 stages:

- Descriptive statistics

The number and percentage of patients approached, enrolled, withdrawn early, and who completed the entire trial will be provided. A CONSORT diagram will be created.

A general description of the population will be provided. For categorical variables, the total number of subjects and the number in each category, as well as the corresponding proportions and their confidence intervals, will be provided. For continuous variables, the sample size, mean, and standard deviation will be provided for normally distributed variables; the sample size, median, and first and last quartile limits will be provided for non-normal distributions. Ordinal variables will be analyzed as categorical variables (sample size and percentage) to better clarify the available data.

- Study Design

This is an exploratory study of a sample, without a comparison group. The primary endpoint is based on a binary qualitative variable (yes/no). The statistical method selected is based on estimating a population proportion with a 95% confidence interval. For secondary endpoint 1 (surgical feasibility), the same type of analysis will be used as above for the primary endpoint. For the other secondary endpoints, the statistical analysis will be primarily descriptive.

- Exploratory analysis

To the extent that the study statistician or investigators deem it helpful in clarifying the results obtained, an exploratory phase may be conducted using bivariate (correlation coefficient) or multivariate (multiple regression, logistic regression, or correspondence analysis) tests to determine the relationships between variables.

This phase will be the subject of a written description that will be appended to the study's statistical analysis plan.

In the analysis report, the tests performed are clearly identified as post-hoc tests. Consequently, the probabilities obtained are for guidance only.

8.2. Estimated number of participants to be included in the study, with statistical justification

This is an exploratory study, which makes it difficult to calculate the number of subjects to include. Based on recruitment capacity, the objective is to quickly determine the value of the method so that, if necessary, a comparative study can be conducted, and to ensure sufficient statistical power. A sample of 50 patients allows, if the proportion is between 0.1 and 0.5, for 95% confidence intervals of a reasonable width (see table below).

Confidence intervals	N	Interval width	Proportion (P)	Lower limit	Upper limit
0.95	50	0.166	0.10	0.017	0.183
0.95	50	0.198	0.15	0.051	0.249
0.95	50	0.222	0.20	0.089	0.311
0.95	50	0.240	0.25	0.130	0.370
0.95	50	0.254	0.30	0.173	0.427
0.95	50	0.264	0.35	0.218	0.482
0.95	50	0.272	0.40	0.264	0.536
0.95	50	0.276	0.45	0.312	0.588
0.95	50	0.278	0.50	0.361	0.639

We will therefore estimate the number of patients needed to obtain 50 informed consents.

8.3. Expected significance level

This is a two-sided significance level of 0.05.

8.4. Statistical criteria for stopping the study

No interim analysis is planned that could lead to the study being discontinued.

8.5. Method for handling missing, unused, or invalid data

No specific method for imputing missing data is planned.

8.6. Management of changes to the initial statistical plan

Any modification to this plan will be documented in writing, stating the reasons for the changes. The analysis plan and, if applicable, the document(s) modifying the initial statistical analysis plan will be appended to the analysis report.

8.7. Selection of subjects to be included in the analyses

All patients approached for the study will be included in the CONSORT diagram for the study.

Any patient in the study population who has signed a consent form, completed the study, and for whom there is no protocol violation likely to critically affect the results of the analysis will be included in the analyses.

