4. EVALUATION CRITERIA

4.1. Primary Endpoint

The primary endpoint is the success of the procedure, defined as the successful selective block of the plantar branches of the tibial nerve, anesthesia of the distal foot while preserving heel sensation, and the absence of paresthesia.

The success of the selective block of the plantar branches of the tibial nerve will be assessed using a sensation score for each branch of the tibial nerve.

A cold test and a touch test will be performed every 10 minutes for 40 minutes following the injection of local anesthetics.

The touch test will be performed using a 2-point sensitivity measurement device (Touch-Test).

The cold test will be performed using a cold roller (Rullo “Oerlikon” nizell.ch).

The tests will be performed on specific areas of the tibial nerve:

- calcaneal branches: calcaneus;
- medial plantar nerve: medial part of the arch of the foot;
- lateral plantar nerve: lateral part of the arch of the foot.

A contralateral assessment will be performed to accurately determine the sensory score.

Score/Contralateral side: 2: normal sensation, 1: decreased sensation, 0: total loss of sensation.

The success of the selective block will be confirmed if the following results are obtained at 40 minutes:

- calcaneal branches = 2
- medial plantar nerve = 0
- lateral plantar nerve = 0

At 40 minutes, a precise mapping of the plantar arch will be performed to determine the exact extent of sensory loss (Figure 4).

The degree of paresthesia during the procedure will be assessed by asking the patient about any sensations of discomfort: tingling, numbness, or other prickling sensations.

[figure not shown]

Figure 4: Example of a plantar arch mapping

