5.3. Study Design

Steps	Inclusion Visit		Day 0 In the operating room	Day 15±4	Follow-up visit with the surgeon at 1 month
	Anesthesia consultation	Pre- anesthesia visit			
Information	X				
Consent		X			
Verification of inclusion and exclusion criteria	X	X			
Specific plantar nerve block			X		
Sensory tests			X		
ENR-Plantar nerves			X		
ENA-VVP ENA-ALR ENA-Satisfaction			X		
List of possible complications			X	X (phone call)	X

5.4. Expected duration of participant involvement, description of the timeline and duration of the study

The study itself begins when the patient and the investigator sign the consent form. It ends after checking for complications during the follow-up visit with the surgeon 1 month post-surgery.

The study is scheduled to take 24 months to complete, starting from the date of the first enrollment. The enrollment period is expected to last 23 months.

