5.6. Description of measures taken to reduce or avoid bias

To avoid selection bias, this study will be offered to all eligible patients seen in the anesthesia clinic. For eligible patients who are not included, the reason for exclusion will be noted.

The evaluation criterion is sufficiently objective to avoid any assessment bias.

5.7. Description of the rules for permanently or temporarily terminating a person's participation in the research, procedures for monitoring these individuals, and procedures for replacing these subjects, if necessary

Any subject included in the study may decide to withdraw their consent to participate in the study at any time and for any reason, without having to provide explanations or justifications and without this affecting the care they are receiving or will receive. The investigator must indicate in the patient's eCRF the date and, if applicable, the reason for the termination of participation in the research. Withdrawal of consent prohibits the use of medical data obtained after the withdrawal of consent. Data already collected regarding the subject may be used.

The investigator may temporarily or permanently suspend a subject's participation in the research for any reason that impacts their safety or that is in the patient's best interest. Data already collected regarding the subject may be used in the analysis of the study results.

A subject's withdrawal from the study will not alter their usual care.

A patient who withdraws prematurely from the study will be replaced, and a study withdrawal form will be completed, including the reason for withdrawal (Consort flow diagram).

Once the protocol-specified sample size is reached, the investigator must halt recruitment for the study. However, patients who have already signed a consent form may still be included in the study.

5.8. Identification of all data collected directly in the study's eCRF and for which no other source documents exist

Sensory scores, assessment of plantar nerve recognition, patient satisfaction and comfort scores, as well as data obtained during the telephone call on Day 15±4 by a healthcare professional, are recorded directly in the eCRF.

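### The only analysis set requires reaching the 1-month visit with no critical violation, and post-block withdrawals are replaced, although block success is settled at 40 minutes on Day 0

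*Combined protocol and SAP*

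**What the plan says.** Section 8.7 defines one set for all analyses. Beyond signed consent, a patient must have "completed the study, and for whom there is no protocol violation likely to critically affect the results of the analysis will be included". No set of all treated patients is defined; everyone approached appears in the CONSORT diagram, but only there.

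Section 5.4 fixes the end of the study: "It ends after checking for complications during the follow-up visit with the surgeon 1 month post-surgery".

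The primary outcome comes much earlier. Section 4.1 states: "The success of the selective block will be confirmed if the following results are obtained at 40 minutes". Paresthesia, the other component of success, is asked about during the procedure.

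On exits, section 5.7 states: "A patient who withdraws prematurely from the study will be replaced". It sets no time limit and no cap. It also provides that "The investigator may temporarily or permanently suspend" a participant for reasons of safety or the patient's interest, and then adds: "Data already collected regarding the subject may be used in the analysis of the study results". A similar permission covers data obtained before withdrawal of consent.

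Section 8.5 states: "No specific method for imputing missing data is planned". Section 8.2 builds its precision table on N = 50 and closes with: "We will therefore estimate the number of patients needed to obtain 50 informed consents".

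**The concern.** An outcome known within an hour of injection should not depend on attendance a month later. Under 8.7 it does, so valid primary results can be discarded. Section 5.7 then lets a new patient take the place of one who has already been treated and scored.

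The protocol contains one plausible link between failure and exit. Absence of paresthesia is part of success (4.1), section 5.2.2 treats paresthesia as a sign of nerve damage, and 5.7 allows suspension on safety grounds. A patient who fails through paresthesia could therefore be suspended, not complete the study, and fall outside 8.7.

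The result of this single-arm study is one proportion with its 95% confidence interval (8.1), and 8.2 says it will inform whether a comparative study follows. No comparator would reveal a shifted denominator. Safety is part of the primary objective (3.1) and complications are secondary objective 4 (3.2). Day-0 and Day-15 complication data from non-completers would be lost under the same rule.

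**Working it through.** **The plan's own figures.** Section 8.2 uses the Wald interval, p ± 1.96·√(p(1−p)/50). At p = 0.50 the half-width is 1.96·√(0.25/50) = 0.139, giving 0.361 to 0.639, as printed. All nine rows reproduce; the printed widths are twice the rounded half-width (0.278 here).

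**Inputs not in the documents.** The plan gives neither an expected success rate p nor the share f of failures that leave the analysis. Both are assumed below, and successes are taken not to leave unless stated.

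**Failures leave and are not replaced.** Reported rate = S/(50 − k), with S successes and k failures lost.
- S = 30: 30/50 = 60.0% (Wald 46.4–73.6%). With k = 2, 30/48 = 62.5%; with k = 5, 30/45 = 66.7% (52.9–80.4%); with k = 10, 30/40 = 75.0%.
- At lower rates the shift for k = 5 is smaller: 5/45 = 11.1% instead of 10%, 15/45 = 33.3% instead of 30%, 25/45 = 55.6% instead of 50%.

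**Failures leave and are replaced until 50 are analysed.** If replacements are subject to the same exit, the expected reported rate is p / [p + (1 − p)(1 − f)].

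| True p | f = 10% | f = 20% | f = 30% | f = 50% |
|---|---|---|---|---|
| 0.50 | 52.6% | 55.6% | 58.8% | 66.7% |
| 0.60 | 62.5% | 65.2% | 68.2% | 75.0% |
| 0.70 | 72.2% | 74.5% | 76.9% | 82.4% |
| 0.80 | 81.6% | 83.3% | 85.1% | 88.9% |

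The smallest rise is 81.6 − 80.0 = 1.6 points and the largest 66.7 − 50.0 = 16.7 points.

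**One round of replacement.** Start with 30 successes and 20 failures. Five failures leave and are replaced by 3 successes and 2 failures. Reported: 33/50 = 66.0% (Wald 52.9–79.1%). All treated: 33/55 = 60.0% (47.1–72.9%).

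**Loss in both groups, no replacement.** With true p = 0.70, 5% of successes lost and 30% of failures lost: 0.70·0.95 / (0.70·0.95 + 0.30·0.70) = 0.665/0.875 = 76.0%.

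**Loss unrelated to outcome.** If successes and failures leave at the same rate, the expected reported rate equals p. Only precision suffers: with 45 analysed at p = 0.50 the width is 2·1.96·√(0.25/45) = 0.292, against 0.278 in the plan. This applies only to exclusions that are not replaced; 5.7 replaces withdrawals but does not say that violators or patients lost to follow-up are replaced.

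**The case against.** Several stronger readings are tempting, and the documents do not support them.

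- A reader might infer that a failed block removes the patient from the analysis. It does not do so by rule. Section 5.2.2 prescribes the standard technique when the block fails, 12.5 records its use as data, and under 4.2 the need for an additional technique is failure on secondary endpoint 1. A step the protocol prescribes is not naturally a violation, and a converted patient can still attend at 1 month.
- A reader might infer that missing the Day-15 call means exclusion. Section 5.4 ends the study at the 1-month visit, and nothing makes the call a condition of completion.
- A reader might infer that violations are judged with the outcome known. Section 8.7 does not say when or by whom. The valid criticism is that it is silent and gives no list, in an open-label study.
- A reader might infer that the success rate will be inflated. That needs exit to be more likely after failure. A patient whose heel score fell below 2 but whose forefoot was well anaesthetised has no evident reason to miss a visit a month later.

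There is also mitigation. Section 5.7 permits use of data already collected, 8.1 reports the numbers withdrawn and completed, and withdrawal reasons are recorded. The study is an exploratory pilot with no success threshold.

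What remains is the mismatch itself. The permission in 5.7 is optional and does not override 8.7. The flow counts show that patients left but do not restore their outcomes to the denominator.

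**Conclusion.** The point holds as a defect in the analysis-set and replacement rules. Read literally, 8.7 discards complete 40-minute results, and earlier complication data, from patients who do not reach the 1-month visit. Section 5.7 replaces withdrawals even after the block, and its wording on collected data contradicts 8.7, so the handling of these patients is left open.

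The direction of any bias is conditional. With exit concentrated among failures, the range of about 2 to 17 points rests on assumed true rates of 50–80%, 10–50% of failures leaving, no successes leaving, and replacement under the same exit process. The upper end requires half of all failures to go. At p = 0.60 and f = 20% the rise is about 5 points, against a Wald half-width of 13.6 points at n = 50. With loss unrelated to outcome the bias is zero. The documents do not show which case applies, which is why the rule should be settled before analysis.

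**What to change.** - **Section 8.7.** Define the primary set, also used for secondary endpoint 1, as every consented patient in whom the plantar block was attempted, whatever the later follow-up. Count abandoned blocks and conversions as failures. Describe complications in all patients who received any study block.
- **Section 5.7.** Replace only patients who leave before the block is attempted. Reconcile the optional wording on data already collected with 8.7, so that a treated patient's usable results are always analysed.
- **Section 8.5.** Report missing 40-minute scores with their reasons, and count them as failures at least in a worst-case sensitivity analysis. Making that the primary rule is debatable, because a score missed for logistical reasons would bias the rate downward.
- **Sensitivity analysis.** Keep the set of completers without critical violation for this purpose, with the critical violations listed before analysis.
- **Section 8.2.** State whether the 50 refers to consents or to patients with an attempted block, since the precision table assumes 50 analysed.

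The cost is wording in these sections, with no added procedures. The reported success rate may be slightly lower.

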9. RIGHTS OF ACCESS TO DATA AND SOURCE DOCUMENTS

9.1. Access to Data

The sponsor has obtained the agreement of all parties involved in the research to ensure direct access to all research sites, source data, source documents, and reports for the purpose of quality control and audit by the sponsor and/or the competent authorities.

Investigators shall make the individual documents and data strictly necessary for the monitoring, quality control, and audit of the research available to persons authorized by the sponsor in accordance with applicable laws and regulations (Articles L.1121-3 and R.5121-13 of the Public Health Code).

9.2. Source documents

Source documents are defined as any original document or item that serves to prove the existence or accuracy of data or facts recorded during the research. They shall be retained for 15 years by the healthcare facility where the research was conducted in accordance with regulations.

9.3. Data confidentiality

In accordance with the provisions regarding the confidentiality of data to which persons responsible for quality control of research involving human subjects have access (Article L.1121-3 of the Public Health Code), and in accordance with the provisions regarding the confidentiality of information concerning, in particular, the nature of investigational drugs, trials, the participants, and the results obtained (Article R. 5121-13 of the Public Health Code), individuals with direct access to this data shall take all necessary precautions to ensure the confidentiality of information regarding the participants, particularly with respect to their identity, as well as the results obtained. Those responsible for quality control, just like the investigators themselves, are bound by professional secrecy (under the conditions defined by Articles 226-13 and 226-14 of the Penal Code).

During the course of the research or upon its completion, the data collected on the participants and transmitted to the sponsor by the investigators (or any other specialized personnel) will be anonymized. Patients will be identified only by an identification number containing their initials and their study entry number. These details are recorded in the observation log. The data collected is strictly confidential. It is accessed only by the medical team, persons duly authorized by the study sponsor, and, if necessary, by representatives of the competent health and judicial authorities. The identity of participants will not be disclosed in any report or publication resulting from this study.

The sponsor will ensure that each person participating in the research has given written consent for access to and use of their individual data, which is strictly necessary for the quality control of the research.

The sponsor declares that it will process the study data in accordance with the CNIL's reference methodology (MR001).

10. QUALITY CONTROL AND ASSURANCE

10.1. Quality Control

The sponsor appoints a Clinical Research Associate (CRA) to conduct monitoring visits, who will ensure that:

- the rights, safety, and protection of the individuals participating in the research are upheld,
- the critical elements necessary for the analysis of the primary and secondary objectives are present,
- the reported data are accurate, complete, and consistent with the source documents,
- the research is conducted in accordance with the protocol, Good Clinical Practice (GCP), applicable laws and regulations, and in accordance with the Standard Operating Procedures established by the Research and Innovation Team at CMC Ambroise Paré (RICAP), the study sponsor.

The investigator and members of his team agree to make themselves available during visits conducted by the ARC.

During these visits, the following items will be reviewed:

- Written informed consent;
- Compliance with the research protocol and the technical procedures defined therein;

- Quality of the data collected in the observation log: accuracy, missing data, consistency of the data with the "source" documents (medical records, appointment logs, original laboratory results, etc.).

10.2. eCRF

All information required by the protocol will be recorded in an electronic case report form (eCRF), with data hosted on a central, secure server. Data will be collected as it is obtained by the investigator and/or personnel designated by the investigator.

10.3. Quality assurance

Quality control for the trial is conducted under the responsibility of the Ambroise Paré Clinical Research Center. An audit may be conducted at any time by individuals appointed by the sponsor who are independent of the research team. Except in special cases, the investigator is notified of the planned audit well in advance. The same applies to an inspection conducted by the Competent Authority. The purpose of these procedures is to ensure the quality of the research, the validity of its results, and compliance with applicable laws and regulations.

Those who direct and oversee the research agree to comply with the requirements of the sponsor and the Competent Authority regarding an audit or inspection of the research.

11. ETHICAL CONSIDERATIONS

11.1. Statement indicating that the research will be conducted in accordance with the protocol, good clinical practice, and applicable laws and regulations

The protocol complies with the ethical principles established by the^{18th} World Medical Assembly (Helsinki 1964) and by the amendments established at the^{29th} (Tokyo 1975),^{35th} (Venice 1983),^{41st} (Hong Kong 1989),^{48th} (Somerset West 1996),^{52nd} (Edinburgh 2000),^{53rd} (Washington 2002),^{55th} (Tokyo), 59th (Seoul), and revised at the 64thth World Medical Assembly (Fortaleza, Brazil, October 2013) . It will be conducted in accordance with the ICH guidelines on Good Clinical Practice.

11.2. Procedures for informing and obtaining consent from research participants

No interventional research may be performed on a person without their free and informed consent, obtained in writing after all relevant information has been provided to them orally and prior to any procedure specified in the protocol and related to the research.

The research is presented orally to the patient by an anesthesiologist-investigator during the anesthesia consultation. During this visit, patients will receive complete and honest information, in understandable terms, regarding the study's objectives and constraints, the potential risks involved, the necessary monitoring and safety measures, their right to refuse to participate in the study, and the possibility of withdrawing at any time without this affecting the care they receive. An information sheet corresponding to the information provided to the patient is given to the patient. After answering any questions the patient may have, and after ensuring that the patient has had sufficient time to reflect, the patient's consent is obtained by the anesthesiologist-investigator prior to the patient's inclusion in the study, during the pre-anesthesia visit.

A copy of the consent form, dated and signed by the participant and the investigator, is provided to the participant prior to their participation in the study. The investigator retains the original copy of the dated and signed informed consent form. At the end of the study, a copy of the signed consent form will be

placed in a tamper-proof, sealed envelope containing all consent forms, which will be archived by the sponsor.

Changes to the protocol that result in an amendment will be reflected by corresponding changes in the informed consent form and the information provided verbally to the patient.

